4. STUDY POPULATION

4.1. Number of Subjects

Phase 1: Up to 12 subjects to identify the MTD, but the MTD may be reached with as few as 5 subjects. Subjects enrolled to Phase 1 or Phase 2 who are unable to tolerate cabozantinib monotherapy will not be considered evaluable for the Phase 1 or 2 component of the study and will be replaced. Subjects enrolled to Phase 1 who withdraw for reasons other than toxicity during the DLT Period will be considered not evaluable and will be replaced.

Phase 2: An anticipated 34 subjects will accrue in Phase 2 of study.

Assuming a 10% drop-out/non-evaluable rate, 44 total subjects would be accrued to the efficacy component for the study to yield 40 evaluable subjects. Subjects enrolled to Phase 2 who withdraw prior to initiation of radiation therapy will be determined to be not evaluable and replaced.

4.2. Inclusion Criteria

A subject will be eligible for inclusion in this study only if all the following criteria are met:

1. Subjects, ≥ 18 years old, must have a histologically confirmed diagnosis of sarcomas of the extremities (which may include gluteal muscle involvement) for which neoadjuvant radiation therapy followed by surgical resection is a planned intervention.
 - a. Subjects whose bowel cannot be completely protected from radiation exposure due to primary tumor location (e.g., proximal lower extremity) will be excluded.
2. Subjects must have one or more measurable target lesions by RECIST v1.1, assessed via CT scan or MRI.
3. At the time of study enrollment, subjects must have a tumor burden that is judged to be surgically resectable.
4. Subjects must have adequate organ function and blood chemistry and blood count parameters:
 - a. Absolute neutrophil count (ANC) $\geq 1500/\text{mm}^3$ ($\geq 1.5 \text{ GI/L}$) without granulocyte colony-stimulating factor support in the last 28 days.
 - b. White blood cell count $\geq 2500/\text{mm}^3$ ($\geq 2.5 \text{ GI/L}$).
 - c. Platelets $\geq 100,000/\text{mm}^3$ ($\geq 100 \text{ GI/L}$) without transfusion in the last 28 days.
 - d. Hemoglobin $\geq 9 \text{ g/dL}$ ($\geq 90 \text{ g/L}$) without transfusion in the last 28 days.
 - e. Alanine aminotransferase (ALT), aspartate aminotransferase (AST), and alkaline phosphatase (ALP) $\leq 3 \times$ upper limit of normal (ULN).
 - i. ALP $\leq 5 \times$ ULN is permitted in subjects with documented bone metastases (Phase 1 only).
 - f. Total bilirubin $\leq 1.5 \times$ ULN (for subjects with Gilbert's disease $\leq 3 \times$ ULN).
 - g. Serum albumin $\geq 2.8 \text{ g/dL}$.
 - h. Serum creatinine $\leq 2.0 \times$ ULN or calculated creatinine clearance $\geq 30 \text{ mL/min}$ ($\geq 0.5 \text{ mL/sec}$) using the Cockcroft-Gault equation:

Males: $(140 - \text{age}) \times \text{weight (kg)} / (\text{serum creatinine [mg/dL]} \times 72)$

Females: $[(140 - \text{age}) \times \text{weight (kg)} / (\text{serum creatinine [mg/dL]} \times 72)] \times 0.85$

- i. Urine protein/creatinine ratio (UPCR) $\leq 1 \text{ mg/mg} (\leq 113.2 \text{ mg/mmol})$.
5. Eastern Cooperative Oncology Group (ECOG) performance status 0 or 1.
6. Male or non-pregnant and non-breast feeding female:
 - a. Females of child-bearing potential (FOCBP) must agree to use highly effective contraception without interruption from initiation of therapy and continue until 4 months (120 days) after last dose of study therapy. FOCBP must have a negative serum pregnancy test (β -hCG) result at screening and agree to ongoing pregnancy testing during the study, and at the end of study treatment. A highly effective method of contraception is defined as one that results in a low failure rate (that is, $<1\%$ per year), when used consistently and correctly, such as implants, injectables, combined oral contraceptives, some intrauterine contraceptive devices, sexual abstinence, or a vasectomized partner (APPENDIX 1 - WOMEN OF CHILDBEARING POTENTIAL DEFINITIONS AND METHODS OF CONTRACEPTION).
 - b. Male subjects must practice abstinence or agree to use a condom during sexual contact with a pregnant female or a female of childbearing potential while participating in the study (APPENDIX 1 - WOMEN OF CHILDBEARING POTENTIAL DEFINITIONS AND METHODS OF CONTRACEPTION).
7. Life expectancy of >3 months, as determined by the investigator.
8. Ability to understand and sign informed consent.
9. Willingness and ability to comply with scheduled visits, laboratory tests, and other study procedures.

4.3. Exclusion Criteria

A subject will not be eligible for inclusion in this study if any of the following criteria apply:

1. Receipt of any type of cytotoxic, biologic, or other systemic anticancer therapy (including investigational) for the investigational diagnosis.
2. Receipt of any prior radiation therapy for the investigational diagnosis.
3. Known central nervous system (CNS) metastases.
4. Concomitant anticoagulation with oral anticoagulants (e.g., warfarin, direct thrombin and Factor Xa inhibitors) or platelet inhibitors (e.g., clopidogrel). Allowed anticoagulants are the following:
 - Low-dose aspirin for cardioprotection (per local applicable guidelines) is permitted.
 - Low-dose low molecular weight heparins (LMWH) are permitted.

- Anticoagulation with therapeutic doses of LMWH is allowed in subjects without known brain metastases who are on a stable dose of LMWH for at least 6 weeks before first dose of study treatment, and who have had no clinically significant hemorrhagic complications from the anticoagulation regimen or the tumor. Subjects with hemoptysis, central nervous system hemorrhage or gastrointestinal hemorrhage within the last 6 months prior to treatment are excluded.
- 5. The subject has uncontrolled, significant intercurrent or recent illness including, but not limited to, the following conditions:
 - Cardiovascular disorders:
 - i. Congestive heart failure New York Heart Association Class 3 or 4, unstable angina pectoris, serious cardiac arrhythmias.
 - ii. Uncontrolled hypertension defined as sustained blood pressure (BP) > 150 mm Hg systolic or > 100 mm Hg diastolic despite optimal antihypertensive treatment.
 - iii. Stroke (including transient ischemic attack [TIA]), myocardial infarction (MI), or other ischemic event, or thromboembolic event (e.g., deep venous thrombosis, pulmonary embolism) within 6 months before first dose. Uncontrolled serious medical or psychiatric illness.
 - Gastrointestinal (GI) disorders including those associated with a high risk of perforation or fistula formation:
 - i. The subject has evidence of tumor invading the GI tract, active peptic ulcer disease, inflammatory bowel disease (e.g., Crohn's disease), diverticulitis, cholecystitis, symptomatic cholangitis or appendicitis, acute pancreatitis, acute obstruction of the pancreatic duct or common bile duct, or gastric outlet obstruction.
 - ii. Abdominal fistula, GI perforation, bowel obstruction, or intra-abdominal abscess within 6 months before first dose.
 - iii. Note: Complete healing of an intra-abdominal abscess must be confirmed before first dose.
 - Clinically significant hematuria, hematemesis, or hemoptysis of > 0.5 teaspoon (2.5 ml) of red blood, or other history of significant bleeding (e.g., pulmonary hemorrhage) within 12 weeks before first dose.
 - Cavitating pulmonary lesion(s) or known endotracheal or endobronchial disease manifestation.
 - Lesions invading or encasing any major blood vessels.
 - Other clinically significant disorders that would preclude safe study participation.
 - i. Serious non-healing wound/ulcer/bone fracture.

- ii. Uncompensated/symptomatic hypothyroidism.
- iii. Moderate to severe hepatic impairment (Child-Pugh B or C).

6. Major surgery (e.g., GI surgery, removal or biopsy of brain metastasis) within 8 weeks before first dose of study treatment. Complete wound healing from major surgery must have occurred at least 30 days before first dose, and from minor surgery (e.g., simple excision, tooth extraction) at least 10 days before first dose. Subjects with clinically relevant ongoing complications from prior surgery are not eligible.
7. Corrected QT interval calculated by the Bazett's formula (QTc) > 480 ms per electrocardiogram (ECG) within 28 days before first dose of study treatment.
 - Note: If a single ECG shows a QTc with an absolute value > 480 ms, two additional ECGs at intervals of approximately 3 min must be performed within 30 min after the initial ECG, and the average of these three consecutive results for QTc will be used to determine eligibility.
8. Pregnant or lactating females.
9. Inability to swallow tablets.
10. Previously identified allergy or hypersensitivity to components of the study treatment formulations.
11. Diagnosis of another malignancy within 2 years before first dose of study treatment, except for superficial skin cancers, or localized, low-grade tumors deemed cured and not treated with systemic therapy.
12. Concurrent use of medications (especially those interacting with CYP3A417) that potentially interact unsafely with cabozantinib which cannot be discontinued or substituted
13. Subjects with a sarcoma which has other, defined treatments or biology distinctly different from those of soft tissue sarcomas in general. Including, but not limited to, Ewing's sarcoma, rhabdomyosarcoma, gastrointestinal stromal tumors, Kaposi's sarcoma, Wilms' tumor.
14. Transfusion of blood product or G-CSF support factor within the last 28 days.
15. Recent infection requiring systemic anti-infective treatment that was completed ≤ 14 days prior to enrollment (except for uncomplicated urinary tract infection or upper respiratory tract infection).

5. TABLE OF EVENTS

The schedule of assessments in Table 2 outlines the specific time points for study assessments.

Table 2. Schedule of Assessments

Assessments ^a	Baseline Screening ^b	Treatment Phase Cycle 1-3			Treatment Phase Cycle 4+	End of Treatment (EOT) Visit ^d	30 Day Safety Follow-Up ^p	Survival Follow-up
		D1	D8 ^c	D15 ^c	D1		(+/- 7 d)	
Informed Consent	X							
Medical History	X							
Hepatitis and HIV Screen ^e	X							
Urinalysis w/micro	X	X	X	X	X	X		
Urine Protein / Creatinine Ratio ^q	X							
TSH, Free T4	X	X			X	X		
Pregnancy Test ^f	X	X			X	X		
LVEF (echo or MUGA)	X							
12-lead ECG	X	X			X	X	X	
Physical Exam/ECOG	X	X	X	X	X	X	X	
Vital Signs, height, and weight ^g	X	X	X	X	X	X	X	
CBC/Diff/Blood Chem ^e	X	X	X	X	X	X	X	
Lipid Panel ^m	X	X			X	X		
Tissue Sample ⁿ	X ⁿ					X ⁿ		
Imaging ^h	X	Every 12 weeks (\pm 2 week).						
Cabozantinib ⁱ		Daily						
Radiation Therapy ^r		Administered per SOC. Radiation therapy to initiate within +7 days of C1D8.						
AE/Con Med Assessment ^j	X	Continuous from C1D1 through 30-day follow-up.						
Long Term Follow-up ^k								X

^a All treatment visits are allowed to occur in a window of ± 3 days unless otherwise specified.

^b Baseline screening visit will be done within 28 days prior to enrollment.

^c Day 8 and Day 15 visit is only in Cycle 1-3. Cycle 4+ will have visits on Day 1 only.

^d End of Treatment (EOT) Visit should be within 7 days of last study treatment (± 3 days).

^e Baseline HIV and Hepatitis screening to include HIV, HBV sAg, HBV cAb, and HCV Ab. See Table 3 for full Analyte Listing for CBC and chemistry panels.

^f For all female subjects of childbearing potential (see Inclusion 6), a serum pregnancy test will be done at all indicated timepoints. Pregnancy tests conducted after screening will be recorded in the source documentation only.

^g Height is measured only at screening. Vitals signs to include respiration rate, temperature, systolic/diastolic blood pressure, and pulse.

^h Baseline scans should be done within 28 days prior to enrollment, preferably as close to C1D1 as possible. Repeat imaging should be completed every 12 weeks from C1D1 (+/- 2 weeks) for one year after initiation of protocol therapy based on the date of the C1D1 visit, or until disease recurrence/progression, withdrawal of consent, death, or end of study (whichever comes first) regardless of missed or out of window doses. MRI may be used if CT is contra indicated for a subject. The same mode of imaging at screening must be used consistently throughout the study. Baseline imaging must include CAP and the affected extremity. If subjects do not have disease in the A/P, imaging moving forward after baseline may omit those areas.

ⁱ Cabozantinib will be administered daily. Subjects will complete a daily drug diary during treatment, to be reviewed on Day 1 of each cycle. Subjects with at least stable disease at the first post-RT imaging timepoint may continue to receive cabozantinib therapy for a maximum of 6 cycles, with treatment ending at least 28 days prior to any scheduled surgery, including dental surgery.

^j Prior and concomitant medications, as well as any recent procedures should be documented at baseline. Prior medications/procedures include any medications or procedures completed ≤ 28 days prior to informed consent.

^k Follow up will continue to monitor disease status by imaging assessment of, at minimum, CT Chest and the affected extremity approximately every 12 weeks (± 2 weeks), until either one (1) year has elapsed since initiating cabozantinib therapy based on the date of the C1D1 visit, death, withdrawal of consent, disease recurrence, or the study closes, whichever is the earliest. Thereafter, subjects will be followed for survival every 6 months (+/- 1 month) until 3 years have elapsed since initiating cabozantinib therapy based on the date of the C1D1 visit, disease recurrence, end-of-study, death, or withdrawal of consent, whichever is earliest. This evaluation may be made by review of publicly available information, record review and/or telephone contact.

^m Lipid panel should be fasting.

ⁿ Optional tissue samples will be collected from archival tissue. Pre-treatment tissue should have been collected within 12 months prior to initiating protocol therapy. End of Treatment tissue samples may be collected from surgical resection, if applicable. If there is no surgical resection for any reason, end of treatment tissue samples will not be collected. No biopsies will occur solely for research collection.

^p 30 Day Follow-Up visit must occur 30 days from the date that the subject was last administered cabozantinib therapy. This visit has a window of +/- 7 days.

^q If urine protein/creatinine ratio is abnormal, a 24-hour urine collection should be collected for repeat UPC Ratio.

^r Radiation therapy may not be initiated prior to Cycle 1 Day 8. Radiation therapy must initiate within +7 days of the Cycle 1 Day 8 visit. All treatment plans for subjects that are not treated at the main study site will be submitted for review to the Sponsor-Investigator at least 1 week prior to the subject starting radiotherapy. It is recommended that outside treatment plans are received and reviewed as part of study eligibility and screening review. Review and approval of treatment plans for subjects receiving radiotherapy locally must be reviewed and approved by a radiation oncologist sub-investigator prior to initiation of radiotherapy.

6. PROCEDURES

6.1. Screening Evaluations

This study will be conducted at the University of Washington, Seattle, USA. Each subject who enters into the screening period for the study receives a unique subject identification number before any study-related procedures are performed. The subject identification number will be assigned. This number will be used to identify the subject throughout the clinical study and must be used on all study documentation related to that subject.

The subject identification number must remain constant throughout the entire clinical study; it must not be changed after initial assignment, including if a subject is rescreened.

Before subjects may be entered into the study, Exelixis requires a copy of the sites' written IRB/IEC approval of the protocol, informed consent form, and all other subject information and/or recruitment material, if applicable. A signed and dated Institutional Review Board (IRB) approved informed consent form (latest approved version) must be obtained from each subject prior to performing any study-specific procedures. All subjects or legally acceptable representatives must personally sign and date the consent form before commencement of study-specific procedures. Adverse events are to be collected for a subject once they have signed the informed consent.

Screening evaluations will be performed for all subjects to determine study eligibility. These evaluations must be obtained ≤ 28 days prior to enrollment, unless otherwise indicated. Baseline imaging should be obtained as close to initiation of protocol therapy as possible.

The following procedures are to be completed during the 28-day screening period, after signed informed consent has been obtained, designated in the Schedule of Assessments found in Table 2.

- Demographics (if allowed by local regulations, date of birth, sex, race, and ethnicity)
- Physical examination (including physical exam, medical/cancer history, ECOG performance status assessment)
- Prior/concomitant medications and procedures evaluation: all medications taken, and procedures completed within ≤ 28 days prior to signing of informed consent
- Vital signs (height [screening only], weight, temperature, sys/dias blood pressure, respiration rate, and pulse)
- 12-lead Electrocardiogram single tracing
- Left ventricular ejection fraction (LVEF, by echocardiogram or MUGA)
- Adverse event assessment
- Local Laboratory Assessments: blood chemistry, complete blood count (CBC) + differential, complete urinalysis with microscopic evaluation, urine protein/creatinine ratio (UPCR), pregnancy test (women of child-bearing potential), HIV, hepatitis B surface antigen, hepatitis C antibody, fasting lipids, thyroid function

- CT or MRI must be done within the 28-day screening period, but preferably should be done as close to enrollment as possible
- Archival tissue collection (optional)

A subject is considered enrolled when the investigator decides that the subject has met all eligibility criteria. The investigator is to document this decision and date, in the subject's medical record and/or in/on the electronic case report form (eCRF). Subjects should initiate treatment within 14 days of being enrolled to the study (28-day screening window from date of consent to enrollment date, plus up to an additional 14 days from enrollment date to C1D1 [total elapsed time from initiating screening to initiating therapy may not exceed 42 days]).

6.2. Treatment Period

A subject is considered on treatment on study day 1 when the IP, cabozantinib, is first administered. Subjects should initiate treatment within 14 days of being enrolled to the study. Cabozantinib is to be administered after all other protocol-specified pre-dose assessments have been performed during each visit that it is required. Subjects will continue therapy until completion of planned course of treatment, disease progression, or unacceptable AEs. Subjects should be instructed to immediately inform the principal investigator (PI) of any AEs. Subjects experiencing dizziness, sleepiness, or other symptoms that could influence alertness or coordination should be advised not to drive or operate other heavy machinery.

6.2.1. Duration of Treatment

One week of neoadjuvant therapy with cabozantinib will be administered prior to initiation of radiotherapy. Initiation of radiation therapy should occur within +7 days of C1D8.

Typically, RT regimens for neoadjuvant treatment of STS are 5-6 weeks, though may vary based on institutional preference. Typically, an interval of 4-6 weeks exists between completion of RT and time of surgery. Subjects with at least stable disease at the first post-RT imaging timepoint may continue to receive cabozantinib therapy for a maximum of 6 cycles, with treatment ending at least 28 days prior to any scheduled surgery, including dental surgery.

6.2.2. Day 1 Assessment

The following assessments will be performed on Day 1 of each cycle, unless otherwise specified:

- Physical examination
- Concomitant medication and procedures evaluation
- Vital signs (weight, temperature, sys/dias blood pressure, respiration rate, and pulse)
- ECOG performance status
- CBC, differential
- Clinical chemistry panel including fasting lipid panel and thyroid function tests
- Serum pregnancy test (women of child-bearing potential only)
- ECG

- Urinalysis with microscopic evaluation
- Adverse Event assessment

All Day 1 evaluations for Cycle 1 may be omitted if screening evaluations are performed within 72 hours of Cycle 1 Day 1.

6.2.3. Day 8 Assessment

The following assessments will be performed on Day 8 of Cycles 1-3 only:

- Physical evaluation
- Vital signs (weight, temperature, sys/dias blood pressure, respiration rate, and pulse)
- Urinalysis with microscopic evaluation
- Concomitant medication and procedures evaluation
- ECOG performance status
- CBC, differential
- Clinical chemistry panel (Day 8 assessments do not include fasting lipid or thyroid studies)
- Adverse Event assessment

6.2.4. Day 15 Assessment

The following assessments will be performed on Day 15 of Cycles 1-3 only:

- Physical evaluation
- Vital signs (weight, temperature, sys/dias blood pressure, respiration rate, and pulse)
- Concomitant medication and procedures evaluation
- ECOG performance status
- CBC, differential
- Urinalysis with microscopic evaluation
- Clinical chemistry panel (Day 15 assessments do not include fasting lipid or thyroid panel)
- Adverse Event assessment

Table 3. Analyte Listing

Chemistry	Hematology	Urinalysis	Other Labs
Sodium	WBC	Specific gravity	Pregnancy test (WOCBP only)
Potassium	RBC	pH	HIV
Bicarbonate	Hemoglobin	Blood	HBV sAg
Chloride	Hematocrit	Protein	HBV cAb
Total protein	MCV	Glucose	HCV Ab
Albumin	MCH	Ketones	Total Cholesterol
Calcium	MCHC	Microscopic	HDL
Glucose (fasting)	RDW		LDL
BUN	Platelets		Triglyceride
Creatinine	Differential:		TSH, Free T4
Total bilirubin	-Neutrophils		
Alkaline phosphatase	-Lymphocytes		
AST (SGOT)	-Monocytes		
ALT (SGPT)	-Eosinophils		
Amylase	-Basophils		
Lipase			
GGT			
Lactate			
Dehydrogenase			

6.2.5. Disease Assessment

Disease status will be assessed by CT or MRI scan. At baseline, imaging must include chest, abdomen, and pelvis (CAP), in addition to pertinent area of the extremity being treated (per institutional guidelines). If no disease is present in the abdomen/pelvis, these areas may be excluded from repeat imaging. Image preparation and evaluation will follow the specifications provided in the RECIST version 1.1. The same modality (CT or MRI) must be used at screening and throughout the study.

CT/MRI scans to be performed at the following frequency:

- ≤28 days prior to enrollment
- Followed by every 12 weeks (± 2 weeks) from C1D1 for 12 months after initiation of protocol therapy (based on the date of C1D1) until disease recurrence, withdrawal of consent, end of study, completion of protocol participation, or death – whichever occurs first.

An unscheduled scan for suspected disease recurrence/progression may be performed at any time at investigator discretion.

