Follow-up Period	Follow-up period is the on-study time period after the EOT Visit. All subjects that discontinue study drug and have not withdrawn full consent to participate in the study will continue in the follow-up phase for disease recurrence. Follow up will continue approximately every 12 weeks (± 2 weeks), until either one (1) year has elapsed since initiation of cabozantinib therapy (C1D1), death, withdrawal of consent, disease recurrence, or the study closes, whichever is the earliest. This will include a physical exam and imaging assessment. Thereafter, subjects who will be followed every 6 months (+/- 1 month) until 3 years have elapsed since initiation of cabozantinib therapy (C1D1), end-of-study, death, or withdrawal of consent, whichever is earliest. This evaluation may be made by review of publicly available information, record review and/or telephone contact.
Primary Analysis	For this study will occur once all data for primary and secondary endpoints is collected.
Efficacy Analysis Dataset	This includes all subjects treated with at least one dose of cabozantinib at the recommended phase 2 dose, concurrently with neoadjuvant radiation therapy.
Full Analysis Set	All enrolled subjects who receive at least 1 dose of cabozantinib (treated population). Subjects enrolled to Phase 1 who withdraw for reasons other than toxicity during the DLT Period will be considered not evaluable and will be replaced.

Per-protocol Analysis Set	All enrolled subjects who do not have any prospectively defined protocol violations. Subjects enrolled to Phase 1 or Phase 2 who are unable to tolerate cabozantinib monotherapy will not be considered evaluable for the Phase 1 or 2 component of the study and will be replaced. Subjects enrolled to Phase 1 who withdraw for reasons other than toxicity during the DLT Period will be considered not evaluable and will be replaced.
Progression-free survival	The time from the first dose date to the first observation of a disease progression or death due to any cause.
Overall survival	The time from the first dose date to the date of death due to any cause.

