6.4.2. Long Term Follow-Up

Disease status and any subsequent anticancer therapy information status will continue to be monitored. All subjects that discontinue study drug and have not withdrawn full consent to participate in the study will continue in the follow-up phase. Follow up will continue to monitor disease status approximately every 12 weeks (± 2 weeks), until either one (1) year has elapsed since initiating cabozantinib therapy based on the date of C1D1, death, withdrawal of consent, disease recurrence, or the study closes, whichever is the earliest. This will include a physical exam and imaging assessment.

Thereafter, subjects will be followed for survival every 6 months (+/- 1 month) until 3 years have elapsed since initiating cabozantinib therapy based on the date of C1D1, disease recurrence, end-of-study, death, or withdrawal of consent, whichever is earliest. This evaluation may be made by review of publicly available information, record review and/or telephone contact.

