12.2. Efficacy Analysis

Assessment of the primary efficacy analysis will take place in real time. Based on anticipated accrual of 40 evaluable subjects, if 9 or more have relapsed or died due to any cause (unless clearly documented as unrelated to investigational diagnosis, e.g., car accident) at or before one year after cabozantinib initiation, then the study will be closed to further accrual, and data will simply be collected on the remaining subjects, as specified in the protocol.

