An early stopping rule for accrual to the efficacy component of the study is to be undertaken. If 9 (nine) or more evaluable subjects are found to have died or demonstrated disease recurrence at or before 1 (one) year after cabozantinib initiation, then the efficacy component of the study will be discontinued. This assumes of a binomial probability for the primary endpoint, with a target probability of 0.90 for evaluable subjects to be alive and disease-free at one-year after initiation of cabozantinib therapy. When 9 subjects demonstrate failure with respect to the primary endpoint (disease recurrence or death from any cause), then the upper bound of the 95% confidence interval for the binomial probability distribution would no longer encompass the target probability of 0.90 ($31/40=0.775$, 95%CI:0.62-0.89). At this point, the study would be considered negative with respect to the primary endpoint, and further accrual will be discontinued.

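### No scan is required between radiotherapy and surgery, so pre-surgical response can go unmeasured; a minor related point is that the last required scan (weeks 46–50) stops short of the one-year endpoint

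*Combined protocol and SAP*

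**What the plan says.** **Imaging schedule.** Section 6.2.5: "Followed by every 12 weeks (± 2 weeks) from C1D1 for 12 months after initiation of protocol therapy". Table 2 footnote h agrees: "Repeat imaging should be completed every 12 weeks from C1D1 (+/- 2 weeks) for one year after initiation of protocol therapy". Section 6.2.5 adds: "An unscheduled scan for suspected disease recurrence/progression may be performed at any time at investigator discretion". The Follow-up Period definition is looser and omits the C1D1 anchor: "Follow up will continue approximately every 12 weeks"; section 6.4.2 is worded similarly. Visits in that period include an examination and imaging.

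**After one year.** Section 6.4.2: "Thereafter, subjects will be followed for survival every 6 months (+/- 1 month) until 3 years have elapsed". This contact may be by records or telephone. The same section opens: "Disease status and any subsequent anticancer therapy information status will continue to be monitored".

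**What the scans must support.** The Phase II primary endpoint (2.2.1) is relapse at 12 months from treatment start. The nine-failure rule counts relapse or death "at or before one year after cabozantinib initiation" (12.2) and "at or before 1 (one) year after cabozantinib initiation" (12.4). Secondary endpoints (2.2.2) include RECIST 1.1 response before surgery. An exploratory radiomic endpoint (2.2.3) compares baseline images with images taken after RT and before surgery.

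**Treatment timing (6.2.1).** RT starts on C1D8 or up to 7 days later and typically lasts 5–6 weeks. Surgery typically follows 4–6 weeks after RT. Cabozantinib may continue after RT only if the first post-RT scan shows stable disease or better, and it must stop at least 28 days before surgery.

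**The concern.** The scans run on a fixed calendar from C1D1, while two of the things they must measure are tied to other moments: the interval between RT and surgery, and the one-year mark.

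The first mismatch matters more. Once the tumour is resected, pre-surgical response cannot be measured, so a scan taken a week too late loses a secondary and an exploratory endpoint for that subject permanently. The loss would fall on subjects who go straight to surgery and not on those who continue the drug, so the subjects with response data need not represent the whole group.

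The second mismatch touches the primary endpoint, but only at its edge. A silent relapse arising after the last required scan and before one year is not looked for, so observed one-year RFS can err only upwards.

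**Working it through.** **1. Surgery against the first scan.** Inputs are from 6.2.1 and 6.2.5.

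- RT starts at week 1–2. Adding 5–6 weeks, RT ends at weeks 6–8.
- Adding 4–6 weeks, surgery falls at weeks 10–14.
- The first scan window is 12 ± 2, which is weeks 10–14.

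The two ranges coincide. The scan is always post-RT on this timeline, but it may fall on either side of surgery. An example that breaks no rule: RT in weeks 1–6, cabozantinib stopped at week 6, surgery at week 10 (28 days later), first scan at week 12. A subject who continues cabozantinib must already have had a post-RT scan, and surgery comes at least 28 days after the last dose, so that subject is covered.

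**2. Last scan against one year.** Required scans fall at weeks 12, 24, 36 and 48. The last window is weeks 46–50; the next would be 58–62, after required imaging ends. Taking a year as 52 weeks, the unscanned stretch is 52 − 50 = 2 to 52 − 46 = 6 weeks.

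**3. The plan's own figures.** For n = 40, 75% against 90%, one-sided alpha 0.10 and power 90%, the exact binomial rule of at least 34 event-free of 40 gives alpha 0.0962 and power 0.9005. For 31/40, the exact 95% interval is 0.615–0.892, which matches the 0.62–0.89 in 12.4. Both reproduce.

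**4. Size of the one-year effect.** Let F be the number of failures among 40, w the week of the last scan, and f the share of failures that only a routine scan would find. The documents do not give f, so a range is shown. With constant hazard (assumed), RFS(w) = 0.75^(w/52), and the apparent failure probability is q = 0.25 − f × (RFS(w) − 0.75). For w = 48, RFS = 0.7668, and missed failures are 40 × f × 0.0168.

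| f | missed failures | P(F ≥ 9) |
|---|---|---|
| 0 (complete ascertainment) | 0 | 0.700 |
| 0.2 | 0.13 | 0.683 |
| 0.5 | 0.34 | 0.656 |
| 1.0 (bound) | 0.67 | 0.610 |

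Sensitivity at f = 1:

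- Every last scan at week 50: 0.33 missed, P = 0.657.
- Every last scan at week 46: 1.01 missed, P = 0.560.
- Hazard starting only at week 12 (assumed): 0.88 missed with week 48, 1.32 with week 46.
- True RFS of 90%, week 48: 0.29 missed.
- A year of 52.18 weeks instead of 52, week 48: 0.70 missed instead of 0.67.

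**The case against.** **On the pre-surgical scan.** The protocol plainly intends one: 6.2.1 uses the first post-RT scan as a decision point and 2.2.3 names imaging before surgery. Section 3.3 expects about five months of treatment, which suggests that continuing cabozantinib is the usual course, and those subjects are covered. Sites may also image before resection anyway. This limits how many subjects are exposed, but it creates no requirement, and the documents do not say how many will go straight to surgery. A reader might infer that pre-surgical response will be missing for most subjects. The documents do not support that: an on-schedule scan can precede surgery, and the RT and surgery timings are described only as typical.

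**On the one-year scan.** With 12-weekly imaging, week 48 is an ordinary stand-in for 12 months. Deaths count (12.2 excepts only those shown to have nothing to do with the sarcoma), relapses found by examination or unscheduled scan count, and disease status goes on being monitored. The looser wording of 6.4.2 would even allow a scan at one year. The 75% null has no stated source; if it came from similar interval scanning, the bias is smaller. Section 12.4 also ranks avoiding false negatives above avoiding false positives. All of this stands, and it is why this part is minor.

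A reader might go further and say that the trial's type I error is inflated beyond its alpha of 0.10. With a cut-off of 34/40 it would move from 0.096 to 0.105, 0.118 or 0.144 (f = 0.2, 0.5, 1). But that cut-off is derived and the protocol states no success threshold. Under its only stated rule, nine or more failures, the chance of not being declared negative at 75% RFS is already 1 − 0.700 = 0.300 with complete data; it becomes 0.317 or 0.344 at f = 0.2 or 0.5. The gap does not invalidate the primary endpoint.

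**Conclusion.** The point holds in two parts of unequal weight.

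1. **Pre-surgical response (the main part).** Nothing requires a scan after RT and before resection, and the first scan window coincides with typical surgery. A compliant subject who does not continue cabozantinib can have no data for the RECIST secondary endpoint or the radiomic endpoint. This follows from the text. How often it will happen is unknown.
2. **One-year status (minor).** The last required scan is 2–6 weeks early. For a week-48 scan the loss is about 0.1–0.3 failures in 40 at 20–50% scan-only and 0.67 at the bound. This rests on constant hazard, true RFS of 75%, an assumed scan-only share, and a null that reflects complete one-year ascertainment.

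The first part should be fixed because the data cannot be recovered later. The second is worth fixing in the same edit.

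**What to change.** **Pre-surgical scan.** In 6.2.5 and Table 2 footnote h, require the first post-baseline scan after the last RT fraction and before surgery, at week 12 ± 2 or earlier if surgery is earlier. State that the last pre-surgical scan is the one used for RECIST response and radiomics, so that subjects who continue cabozantinib are assessed on their latest image before resection.

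**One-year scan.** Respace the same four scans, for example to weeks 12, 25, 38 and 52, so that the last is the 12-month scan. State in 12.2 and 12.4 that its result defines 12-month status. Align 6.4.2, the Follow-up Period definition and Table 2 (imaging row, footnotes h and k).

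**Cost.** These are text edits and no scan is added. Nominal gaps after the first scan become 13, 13 and 14 weeks instead of 12. If the ± 2 window is kept, the longest possible gap is weeks 36 to 54, or 18 weeks, against 16 now. Some relapses will be found slightly later, which affects time to recurrence and the real-time stopping rule a little; unscheduled scans remain available. A final scan at week 50–54 can err either way: at 75% RFS with all failures scan-only, the chance of nine failures would lie between 0.657 (all at week 50) and 0.740 (all at week 54), around the intended 0.700. The present 46–50 window gives 0.560 to 0.657 on the same assumptions. Moving only the week-48 scan to week 52 is less attractive, because it leaves a nominal 16-week gap after week 36.
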